### 8.3.9. Adverse Events of Special Interest

All AESIs must be reported as an AE or SAE following procedures described in [Section 8.3.1](#) through [8.3.4](#). An AESI is to be recorded as an AE or SAE on the CRF. In addition, an AESI that is also an SAE must be reported using the CT SAE Report Form.

Adverse events of special interest include: all medically important events (see [Appendix 3](#)) that are to be reported as an SAE, and any clinical thrombotic event or hypersensitivity events assessed as non-serious AEs.

#### 8.3.9.1. Lack of Efficacy

Not applicable

### 8.3.10. Thrombotic Potential Assessments (ONLY for participants who reach vector-derived FIX:C Activity Levels >150% After the Infusion of PF-06838435)

Based on non-clinical studies in NHPs, the prior Baxter study using hFIX-Padua, and the Phase 1/2a study, it is not predicted that vector-derived FIX:C activity levels >150% of normal will be achieved in this study. However, thrombin-antithrombin levels (TAT) as thrombotic potential will be measured if vector-derived FIX:C activity levels >150% of normal are achieved in any participant during the study. Blood samples for TAT obtained during screening will be used to establish baseline value. Additional testing can be performed upon discussion with the medical monitor including by not limited to D-dimer, TGA, and/or prothrombin fragments 1+2.

### 8.3.11. Medication Errors

Medication errors may result from the administration or consumption of the investigational product by the wrong participant, or at the wrong time, or at the wrong dosage strength.

Exposures to the investigational product under study may occur in clinical trial settings, such as medication errors.

Safety Event	Recorded on the CRF	Reported on the CT SAE Report Form to Pfizer Safety Within 24 Hours of Awareness
Medication errors	All (regardless of whether associated with an AE)	Only if associated with an SAE

Medication errors include:

- Medication errors involving participant exposure to the investigational product;

- Potential medication errors or uses outside of what is foreseen in the protocol that do or do not involve the participant;
- Not performing a flush of the IV line at the conclusion of the IP infusion.

Such medication errors occurring to a study participant are to be captured on the medication error page of the CRF, which is a specific version of the AE page.

In the event of a medication dosing error, the sponsor should be notified within 24 hours.

Whether or not the medication error is accompanied by an AE, as determined by the investigator, the medication error is recorded on the medication error page of the CRF and, if applicable, any associated AE(s), serious and non-serious, are recorded on an AE page of the CRF.

Medication errors should be reported to Pfizer Safety within 24 hours on a CT SAE Report Form **only when associated with an SAE**.

#### **8.4. Treatment of Overdose**

For this study, any dose of PF-06838435 greater than  $5 \times 10^{11}$  vg/kg of the body weight will be considered an overdose.

Sponsor does not recommend specific treatment for an overdose.

In the event of an overdose, the investigator/treating physician should:

- Contact the sponsor's medical monitor within 24 hours.
- Closely monitor the participant for any AE/SAE and laboratory abnormalities.
- Document the quantity of the excess dose as well as the duration of the overdose in the Medication Error CRF.
- Overdose is reportable to Safety **only when associated with a SAE**.

#### **8.5. Pharmacokinetics**

All samples collected from participants for plasma factor IX activity levels as per the [SoA](#) will be analyzed at a certified clinical laboratory by two different one stage assays along with analysis by chromogenic assay. Results will be used to determine vector-derived FIX:C activity level at steady-state (Week 12 and after).

Measurement of the vector-derived FIX:C activity levels may be confounded by exogenous factor replacement because participants are allowed to use factor protein products to treat any bleeding events during the study. Thus, calculation of the vector-derived FIX:C activity levels will take into consideration data entered in the eDiary. As FIX inhibitors or T-cell

mediated immune response may impact the FIX activity levels, this information will also be taken into account while deriving FIX:C activity levels.

- During all study periods, blood samples will be collected for measurement of vector-derived FIX:C as specified in the [SoA](#) section of the protocol.
- Samples collected will be analyzed using a validated analytical method in compliance with standard operating procedures (SOPs). The samples must be processed and shipped as indicated in the instructions provided to the investigator site to maintain sample integrity. Any deviations from the sample handling procedure (eg, sample collection and processing steps, interim storage, or shipping conditions), including any actions taken, must be documented and reported to the sponsor. On a case by case basis, the sponsor may make a determination as to whether sample integrity has been compromised. Any deviation from the specified sample handling procedure resulting in compromised sample integrity will be considered a protocol deviation. These data will not be included in the CSR.

#### **8.5.1. Samples for Vector Shedding Assays**

Samples of plasma, saliva, PBMC, urine, and semen will be collected as specified in the [SoA](#) for analysis of vector shedding.

In the event that a participant is unable to provide any semen for vector shedding over the course of 1 month post-IP infusion, future attempts to provide semen samples can be stopped provided that the participant provides 3 consecutive negative PBMC samples before no longer being required to follow the restrictions within inclusion criteria #5 in [Section 5.1](#).

Some participants (n = 12), who consent to participate in an optional sub-study, are expected to provide additional (2 hours  $\pm$ 30 minutes, 24 hours  $\pm$ 3 hours, 72 hours  $\pm$ 4 hours after completion of IP infusion and IV line flush on Day 1) samples (plasma, PBMC, saliva, semen, and urine).

These samples will be collected as per the instructions provided to the sites to maintain sample integrity for each sample type. Any deviations from that sample handling procedure must be documented and reported to the sponsor.

#### **8.6. Pharmacodynamics**

Pharmacodynamic markers such as thrombin generation assay (TGA) will be measured for all participants. Global hemostasis markers will also be collected ([Appendix 2](#)).

The samples will be collected as per the [SoA](#) and detailed in the Laboratory Manual.

The PD samples must be processed and shipped as indicated in the instructions provided to the investigator site to maintain sample integrity. Any deviations from the PD sample handling procedure (eg, sample collection and processing steps, interim storage, or shipping conditions), including any actions taken, must be documented and reported to the sponsor. On a case by case basis, the sponsor may make a determination as to whether sample

integrity has been compromised. Any sample deemed outside of established stability, or of questionable integrity, will be considered a protocol deviation.

As part of understanding the PD of the investigational product, samples may be used for evaluation of the bioanalytical method, as well as for other internal exploratory purposes. These data will not be included in the CSR.

Samples will be analyzed using a validated analytical method in compliance with applicable SOPs. These data will be used for internal exploratory purposes and will not be included in the CSR.

#### **8.6.1. Samples for FIX Antigen Levels**

Blood samples will be collected per the [SoA](#) and as specified in the Laboratory Manual to measure FIX antigen levels.

#### **8.6.2. Samples for Thrombin Generation**

During all study periods, blood samples (3.5 mL) to provide approximately 600 µL plasma for TGA analysis will be collected into appropriately labeled tubes containing sodium citrate at times specified in the [SoA](#).

Details regarding the collection, processing, storage, and shipping of the blood samples will be provided in the central lab manual.

#### **8.6.3. Samples for D-dimer**

Blood samples will be collected per the [SoA](#) and as specified in the Laboratory Manual to measure D-dimer.

#### **8.6.4. Shipment of Pharmacodynamic Samples**

The shipment address and analytical laboratory contact information will be provided to the investigator site prior to initiation of the study.

### **8.7. Genetics**

#### **8.7.1. Specified Genetics**

A blood sample for DNA isolation will be collected as specified in the Laboratory Manual, only if a participant has not undergone FIX genetic testing in the past or the results of such testing are not available in the source documents. DNA samples will be analyzed for the purpose of determining the underlying FIX gene mutation.

In the event of DNA extraction failure, a replacement genetic blood sample may be requested from the participant.

See [Appendix 5](#) for information regarding genetic research. Details on processes for collection and shipment and destruction of these samples can be found in the Laboratory Manual.

### **8.7.2. Banked Biospecimens for Genetics**

Banked Biospecimen collection is not required for this study.

### **8.8. Biomarkers**

Not applicable.

### **8.9. Health Economics**

Not applicable.

## **9. STATISTICAL CONSIDERATIONS**

### **9.1. Estimands and Statistical Hypotheses**

The details of statistical methodology will be specified in the Statistical Analysis Plan (SAP).

The hypothesis testing of the primary endpoint is listed below.

- To demonstrate non-inferiority (NI) of PF-06838435 to routine prophylaxis on difference in  $ABR_{total}$  (NI margin of 3 bleeds/year) by comparison of post-infusion of PF-06838435  $ABR_{total}$  from Week 12 to Month 15 versus pre-IP infusion  $ABR_{total}$  collected during Pre-Infusion Period, in participants  $\geq 18$  years of age with moderately severe to severe hemophilia B (FIX:C  $\leq 2\%$ ), who have tested negative for nAb and have no medical history of FIX inhibitor. The primary objective for  $ABR_{total}$  will be considered to have been met if non-inferiority is demonstrated. Additionally, if non-inferiority is demonstrated on  $ABR_{total}$ , subsequent testing for superiority will be conducted on the endpoint. Superiority of  $ABR_{total}$  is considered a secondary analysis.

#### **9.1.1. Estimands**

The primary objective is addressed via the primary endpoint of  $ABR_{total}$ . Efficacy by  $ABR_{total}$  is summarized by the difference between pre- and post-treatment with PF-06838435; pre-treatment data will be obtained from the Pre-Infusion Period, including the lead-in Study C0371004. Steady-state FIX:C is a key secondary endpoint and the efficacy by FIX:C is summarized by the steady-state population mean post-treatment compared to a fixed threshold of 5%. Since no more than the single dose of study treatment on Day 1 will be administered during the study, there should be no treatment discontinuations. Resumption of FIX prophylaxis regimen is allowed as detailed in [Section 6.5.1](#) and is assessed directly via secondary endpoints (AIR and FIX consumption). Data following resumption of FIX prophylaxis regimen will be excluded from the analysis of  $ABR_{total}$ . There may be missing data from participants lost to follow-up, but it is anticipated to be rare. The primary endpoint,  $ABR_{total}$  will utilize all applicable data to define the endpoints. A description of the data which are not applicable for  $ABR_{total}$  (eg, data following the resumption of prior prophylaxis therapy) will be discussed in detail in the Statistical Analysis Plan (SAP). Any missing data will not be imputed for the primary endpoint. The method to handle missing data of other endpoints will be discussed in SAP. Baseline for change from baseline analyses will be defined based on the data collection method of each endpoint, but will reflect data before IP infusion.

## 9.2. Sample Size Determination

Participants who complete the lead-in protocol C0371004 will be screened to achieve desired sample size of 40 participants, and eligible participants will be assigned to study intervention. All 40 participants are expected to be evaluable in this one-armed study.

When all 40 participants have completed at least 15 months of follow-up post-infusion of PF-06838435, the  $ABR_{total}$  data will provide at least 90% power (one-sided test with  $\alpha=0.025$ ) to demonstrate non-inferiority of gene therapy compared to prophylaxis treatment on the difference in  $ABR_{total}$ , using a repeated measure negative binomial regression, with a non-inferiority margin of 3.0 bleeds/year. The assumed background rate of annualized bleeding is a conservative 5.0 and the assumed annualized bleeding rate post-PF-06838435 is 1.5. The details of non-inferiority margin selection are included in [Appendix 10](#).

The number of participants may exceed 40, because all participants who complete the lead-in study (C0371004) and meet other eligibility criteria will be allowed to participate in this study.

## 9.3. Populations for Analyses

For purposes of analysis, the following populations are defined:

Population	Description
Enrolled	All participants who sign the ICF and meet all inclusion/exclusion criteria.
Dosed 	All participants enrolled in the study and received IP.
Safety	All participants enrolled in the study and received IP, which is the same as dosed population.
Intent To Treat (ITT)	ITT population is not defined for this study since it is not a randomized study.
Evaluable	All participants are enrolled in the study and take study medication and no significant interruption of efficacy measurement. 

1. Dosed population is the primary analysis population for efficacy endpoint analysis, while evaluable population is the analysis population for sensitivity analysis.
2. Significant interruption will be assessed after discussion between the investigator and the medical monitor, eg, if a participant requires a major surgery, this will be a significant interruption of measurement.

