**Day 1 (at Study Site or at approved Infusion Center)**

Day 1 procedures will be conducted according to the [SoA \(Section 1.3\)](#).

Blood for LFTs are to be drawn and tested locally and centrally prior to dosing participants (up to 3 days prior to Day 1/ Visit 3 is acceptable). Utilize mobile phlebotomy/ home health services as needed, and if possible. Local LFTs are required to be reviewed prior to thawing drug. If the investigator has any clinical concerns regarding the local LFT results, drug should not be thawed. These LFT results may help in the assessment of future LFTs and decisions on when to begin corticosteroid treatment, if necessary. These LFT results should be entered into the CRF as an unplanned visit.

Note: Participants should be informed that alcohol consumption could contribute to abnormally elevated LFT results and thereby delay the infusion of the study drug.

The site staff (or Infusion Center staff) will confirm that the participant is eligible (see [Section 5.1](#) and [5.2](#)) to receive PF-06838435 infusion. Prior to dosing, [Sections 10.13.3](#) and [10.13.4](#) should be considered. The IP should NOT be thawed and prepared without this eligibility confirmation AND affirming that the participant is physically present at the clinic (or infusion center).

Participants are expected to bring their current Factor IX replacement therapy with them.

If the infusion of PF-06838435 is started for a participant and cannot be completed (receives less than the prescribed dose) for any reason, the protocol does not allow for the participant to be rescreened. The participant will be followed for safety; the data obtained from such participant will not be included towards efficacy assessment.

For Japanese sites please refer to Japan appendix, [Section 10.11.1.4](#).

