2.1.1. Primary Estimand(s)

The primary objective is addressed via assessment of the primary endpoint of ABR_{total} from Week 12 to Month 15 after PF-06838435 infusion. Efficacy is summarized by the difference between ABR_{total} pre- and post PF-06838435 infusion; pre-treatment data will be obtained from Pre-Infusion Period. The estimand includes the following 4 attributes:

- Population: male adults with moderately severe to severe hemophilia B (FIX:C $\leq 2\%$) who have received infusion of PF-06838435.
- Variables:
 - ABR_{total} comparing pre PF-06838435 infusion from the Pre-Infusion Period to post PF-06838435 infusion from Week 12 to Month 15.

- Intercurrent event(s): Since no more than the single dose of PF-06838435 infusion on Day 1 will be administered during the study, there should be no treatment discontinuations. Prophylaxis FIX replacement regimen may be resumed if treatment with PF-06838435 is not efficacious. Once prophylaxis FIX replacement is re-established, the data will not reflect the efficacy of study treatment assessments and therefore data following resumption of FIX prophylaxis regimen will be excluded. Further details of handling intercurrent events are discussed in Section 3 for each of the endpoints.
- Population-level summary: difference in mean ABR_{total} pre PF-06838435 infusion vs. ABR_{total} from Week 12 to Month 15.

There may be missing data from participants lost to follow up, but it is anticipated to be rare. The primary endpoint, ABR_{total} from Week 12 [Day 82] to Month 15 [Day 469]) will utilize all applicable data to define the endpoint, with the exceptions as discussed in Section 3. There will be no imputation for missing data for the primary analysis.

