4. ANALYSIS SETS (POPULATIONS FOR ANALYSIS)

This study is an open-label, single-arm study. The populations for analyses are outlined in the table below.

Population	Description
Enrolled	All participants who sign the informed consent form (ICF) and meet all inclusion/exclusion criteria
Dosed	All participants enrolled in the study and who received PF-06838435 infusion
Safety	All participants enrolled in the study and who received PF-06838435 infusion, which is the same as dosed population.
Evaluable	All participants enrolled in the study and who received PF-06838435 infusion and have no significant interruption of efficacy measurement.

The Evaluable analysis population listed above would exclude participants with significant interruption of efficacy measurement, or participants who do not have or have not yet completed 15 months of follow up post PF-06838435 infusion. Significant interruption will be assessed after discussion between the investigator and the medical monitor, e.g., if a participant requires a major surgery, this will be a significant interruption of measurement.

In this study, there are also substudies planned, for which the analysis populations are outlined below.

X-ray Substudy	All dosed participants sign the additional ICF for the X-ray substudy and meet all
Analysis Population	inclusion/exclusion criteria, and the participant's joint images have been
	reviewed.
MRI Substudy	All dosed participants who are dosed and sign the additional ICF for the MRI
Analysis Population	substudy and meet all inclusion/exclusion criteria, and the participant's joint
	images have been reviewed following the extended MRI scale with a final score
	combining soft-tissue and osteochondral sub-scores at baseline, and any data
	post-baseline
Vector Shedding	All dosed participants who sign the additional ICF for the Vector Shedding
Substudy Analysis	substudy and meet all inclusion/exclusion criteria, and who have any additional
Population	vector shedding data

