6.5.2. Study Conduct and Subject Disposition

Participant disposition will be summarized for the Enrolled population. This table will present the count and percentage of participants in each disposition category: number discontinued and reason for discontinuation (including number of screen failure), number completed, and number ongoing. A data listing will be provided along the disposition table.

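### Read literally, the Dosed and Safety sets leave out a participant who was infused and later found to have failed an eligibility criterion

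*Protocol*

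**What the plan says.** Protocol 9.3 builds its analysis sets in a chain. Enrolled is "All participants who sign the ICF and meet all inclusion/exclusion criteria". Dosed is "All participants enrolled in the study and received IP". Safety is "All participants enrolled in the study and received IP, which is the same as dosed population". Evaluable also starts from participants who are enrolled and treated.

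SAP 4 keeps the chain. Enrolled is "All participants who sign the informed consent form (ICF) and meet all inclusion/exclusion criteria", and Safety is "All participants enrolled in the study and who received PF-06838435 infusion, which is the same as dosed population".

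Dosed is the primary efficacy set (Protocol 9.3, footnote 1; SAP 6.1.1.1). All safety analyses use the Safety set (Protocol 9.4.2; SAP 6.6).

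SAP 2.1.1 describes the target population of the primary estimand differently: adult men with the disease as defined, "who have received infusion of PF-06838435". It does not require that every eligibility criterion was met.

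**The concern.** For a treated population, and above all for a safety population, membership should follow from having received the product. Here it also depends on eligibility. Some criteria rest on history, such as a past FIX inhibitor (exclusion 2) or an earlier gene therapy dose (exclusion 12), and an error in history can come to light after the infusion. The product is given once and participants are followed for six years, so there is ample time for such a finding.

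If it happened, the written definitions would remove a treated man from the adverse event, laboratory and other safety tables and from the primary bleeding comparison. Two programmers could also derive different denominators, one applying the definition of Enrolled as written and the other treating everyone infused as enrolled.

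**Working it through.** **Step 1: substitute the definitions** (Protocol 9.3, SAP 4).

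- Enrolled = consent signed AND all criteria met.
- Dosed = Enrolled AND infused = consent signed AND all criteria met AND infused.
- Safety = Dosed.

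A participant who was infused but failed one criterion is outside Enrolled, and so outside Dosed, Safety and Evaluable.

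**Step 2: look for a rule that brings him back.** Three provisions bear on the case: waivers are not permitted (Protocol 5), only enrolled participants may receive the product (Protocol 6.2), and eligibility is confirmed on Day 1 (Protocol 8). All three govern conduct. None says how a participant dosed in breach of a criterion is analysed, and neither document has an all-treated set.

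**Step 3: safety illustration.** The documents give no expected number of violations, so 41 dosed with one ineligible is an assumption. Suppose that participant has the only event of some kind. Exact (Clopper-Pearson) two-sided 95% upper limits:

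- All treated: 1/41 = 2.4%. The limit solves P(X ≤ 1 | n = 41, p) = 0.025, giving 12.9%.
- As written: 0/40 = 0%. The limit is 1 − 0.025^(1/40) = 8.8%.

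**Step 4: efficacy illustration.** Protocol 9.2 assumes 5.0 bleeds/year before infusion and 1.5 after, a planned difference of 1.5 − 5.0 = −3.5. The margin is +3.0, so the distance to it is 3.0 − (−3.5) = 6.5. If the mean change in all 41 is −3.5, removing one participant with change d shifts the simple mean by (−3.5 − d)/40:

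| Pre ABR | Post ABR | d | Shift on exclusion | Effect |
|---|---|---|---|---|
| 5 | 5 | 0 | −0.09 | favours product |
| 5 | 10 | +5 | −0.21 | favours product |
| 5 | 15 | +10 | −0.34 | favours product |
| 15 | 10 | −5 | +0.04 | against product |

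The largest shift shown is 0.34/6.5, about 5% of the distance to the margin. The planned negative binomial model would weight participants differently, so these figures show scale only.

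**Step 5: power.** The documents give no SD for the paired difference. With a normal approximation, Φ(6.5√N/SD − 1.96), going from N = 40 to 39 changes power from 98.4% to 98.2% at an assumed SD of 10. At SD 12.7, the largest that still gives 90% at N = 40, it changes from 90.0% to 89.3%.

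**The case against.** The strongest reply is that Enrolled is meant operationally. Protocol 5.4 describes screen failures as people who consent but do not enter the study, so a man who was entered and infused is not one. Protocol 6.2 treats enrolment as a status held before dosing. SAP 6.5.2 says "Participant disposition will be summarized for the Enrolled population" and then asks that table to include screen failures, which the written definition of Enrolled does not allow for anyone who failed a criterion. The sponsor may therefore intend to analyse everyone infused. That is plausible, but neither document says it, and the definition as written says otherwise.

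It is also true that collection of safety data does not depend on the analysis set. Adverse events are collected from consent, and serious events are reported to the sponsor within 24 hours (Protocol 8.3.1, 8.3.1.1). The gap is in the summaries, not in oversight.

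A reader might infer more than the documents support:

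- **That pre-dose liver tests will routinely create violations.** Exclusions 6 and 7 use central results, while before dosing "Local LFTs are required to be reviewed prior to thawing drug". But repeat central results for eligibility must be available before Visit 2, and eligibility is settled before the product is ordered. The stated purpose of the pre-dose tests is to help interpret later liver tests and time corticosteroids. Nothing says a late central result cancels eligibility retrospectively.
- **That exclusion always favours the product.** It removes the participant's baseline as well, and the last row of the table goes the other way.
- **That exclusions could be chosen with outcomes known, or that ineligible participants are those most likely to be harmed.** The trial is open-label, but the documents describe no such adjudication and give no data on risk in ineligible participants.

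**Conclusion.** The point stands as a defect in the definitions. Read as written, both documents exclude a treated but ineligible participant from the primary efficacy set and from all safety summaries, in conflict with the SAP's own estimand population. It matters only if such a participant occurs. The conduct rules lower that chance without removing it, and the documents give no basis for estimating it.

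The consequence is mainly for safety reporting: under the assumption of one violator among 41 dosed, a single event would disappear from the table and the upper limit would fall by about 4 percentage points. One exclusion would not plausibly decide the non-inferiority test, and its direction cannot be stated in advance. The change is worth making because the rule gives a wrong answer in a foreseeable case and is easily corrected. The documents do not show that the result would be biased.

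**What to change.** In Protocol 9.3 and SAP 4, define Dosed and Safety as all participants who received PF-06838435, regardless of any eligibility deviation identified before or after infusion, and drop the reference to Enrolled. List important eligibility deviations and, if wanted, add a sensitivity analysis without those participants. The new wording should also be reconciled with the Day 1 text in Protocol 8, which keeps data from incomplete infusions out of the efficacy assessment. The Dosed definition does not reflect that rule.

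As a separate, minor correction, base the SAP 6.5.2 disposition table on all participants who signed consent, so that screen failures can be counted.

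The cost is wording in two population tables and one sentence on disposition, with no new data. The downside is that a dosed but ineligible participant, including one who does badly, would count in the primary result. If the sponsor already intends to analyse everyone infused, the edit changes no result and only removes the ambiguity.
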